9.2.3. Follow-up of AEs and SAEs

After the initial AE/SAE report, the investigator is required to proactively follow each participant at subsequent visits/contacts. All SAEs, and non-serious AEs of special interest (as defined in Section 9.2.5), will be followed until the event is resolved, stabilized, otherwise explained, or the participant is lost to follow-up (as defined in Section 8.3). Further information on follow-up procedures is given in Appendix 4.

9.2.4. Regulatory Reporting Requirements for SAEs

- Prompt notification by the investigator to the sponsor of a SAE is essential so that legal obligations and ethical responsibilities towards the safety of participants and the safety of a study treatment under clinical investigation are met.
- The sponsor has a legal responsibility to notify both the local regulatory authority and other regulatory agencies about the safety of a study treatment under clinical investigation. The sponsor will comply with country-specific regulatory requirements relating to safety reporting to the regulatory authority, Institutional Review Boards (IRB)/Independent Ethics Committees (IEC), and investigators.
- Investigator safety reports must be prepared for suspected unexpected serious adverse reactions (SUSAR) according to local regulatory requirements and sponsor policy and forwarded to investigators as necessary.
- An investigator who receives an investigator safety report describing a SAE or other specific safety information eg, summary or listing of SAE) from the sponsor will review and then file it along with the Investigator's Brochure and will notify the IRB/IEC, if appropriate according to local requirements.

9.2.5. Adverse Events of Special Interest (AESI) – Post-Inhalation Cough Immediately Following Dosing

In the Proof-of-Concept (PoC) study PIII16678, which was conducted in 126 randomized participants from a population similar to this protocol and a previous formulation of nemiralisib (DISKUS formulation blended with only one excipient, lactose), there was a higher incidence of treatment-related, mild and moderate adverse events of cough (Preferred Term) reported immediately after dosing in exacerbating subjects in the GSK2269557 DISKUS 1000 mcg QD group (n=22 [35%]) compared exacerbating subjects in the placebo DISKUS group (n=2 [3%]). For the 22 subjects in the GSK2269557 1000 mcg group, the events of cough for 20 of the subjects were considered by the Investigator to be related to study treatment. From the review of reported events, cough often occurred immediately after dosing and in some subjects it seemed to repeat on most of the dosing days. Cough was reported to be generally mild or moderate and resolved after stopping dosing. Three subjects (all in the GSK2269557 DISKUS 1000 mcg QD group) discontinued the study due to cough. Additional details are provided in the Nemiralisib (GSK2269557) Investigator's Brochure.

Therefore, to further evaluate this finding of post-inhalation cough immediately following dosing, during study Visits 2-6 in the 12-Week Double-Blind Treatment Period, Investigators (or medically qualified designees) will monitor participants for potential study treatment tolerability issues, including post-inhalation cough, **within 5 minutes immediately following dosing**. If tolerability issues, including coughing are observed, details will be recorded in the source documentation and eCRF.

The iSRC will have study oversight to ensure that it meets the highest standards of ethics and participant safety and to carry out the planned interim safety data analyses/data reviews as discussed in [Appendix 3](#) and Section 10.3.5. Data (including adverse event reports of post-inhalation cough immediately following study treatment dosing) will be reviewed by the iSRC on a periodic basis, as defined in the iSRC Charter.

9.2.6. Cardiovascular and Death Events

For any cardiovascular events and all deaths, whether or not they are considered SAEs, specific Cardiovascular (CV) and Death sections of the eCRF will be required to be completed. These sections include questions regarding cardiovascular (including sudden cardiac death) and non-cardiovascular death.

The CV eCRFs are presented as queries in response to reporting of certain CV MedDRA terms. The CV information should be recorded in the specific cardiovascular section of the eCRF within one week of receipt of a CV Event data query prompting its completion.

The Death eCRF is provided immediately after the occurrence or outcome of death is reported. Initial and follow-up reports regarding death must be completed within one week of when the death is reported.

9.2.7. Disease-Related Events and/or Disease-Related Outcomes Not Qualifying as SAEs

The following disease related events (DREs) are common in participants with COPD and can be serious/life threatening:

- exacerbation of COPD

Because these events are typically associated with the disease under study, they will not be reported according to the standard process for expedited reporting of SAEs to GSK (even though the event may meet the definition of a SAE). These events will be recorded on the DRE page, in this study the exacerbation page in the participant's eCRF within 72 hours after the Investigator becomes aware of the event. These DREs will be monitored by a Safety Review Team (SRT) on a routine basis.

NOTE: However, if either of the following conditions apply, then the event must be recorded and reported as an SAE (See Section 9.2):

- *The event is, in the investigator's opinion, of greater intensity, frequency, or duration than expected for the individual participant, or*

- *The investigator considers that there is a reasonable possibility that the event is related to study treatment*

If an exacerbation is caused by pneumonia this must be recorded as pneumonia in the AE or SAE form in the eCRF and the pneumonia form in the eCRF (See Section 9.1.2).

9.2.8. Pregnancy

- Details of all pregnancies in female participants will be collected after the start of study treatment and until 14 days after the last dose of study treatment.
- Details of pregnancies for female partners of male participants will not be routinely collected; however, voluntary reports of such incidents will be captured through the GSK standard reporting mechanism.
- If a pregnancy is reported, the investigator should inform GSK within 24 hours of learning of the pregnancy and should follow the procedures outlined in [Appendix 5](#) Abnormal pregnancy outcomes (eg, spontaneous abortion, fetal death, stillbirth, congenital anomalies, ectopic pregnancy) are considered SAE.

9.2.9. Medical Device Incidents (Including Malfunctions)

Medical devices, the study-supplied valved-holding chamber and the clip-on Propeller Sensors to be attached to the double-blind study treatment ELLIPTA inhalers and the study-supplied albuterol [salbutamol] MDIs, are being provided for use in this study for the purposes of standardizing the conduct of the post-bronchodilator FEV₁ measurements and capturing compliance with double-blind study treatment and rescue albuterol [salbutamol] use, respectively. In order to fulfill regulatory reporting obligations worldwide, the investigator is responsible for the detection and documentation of events meeting the definitions of incident or malfunction that occur during the study with such devices.

The definition of a Medical Device Incident can be found in [Appendix 8](#).

NOTE: Incidents fulfilling the definition of an AE/SAE will also follow the processes outlined in Section 9.2 and [Appendix 4](#) of the protocol.

9.2.9.1. Time Period for Detecting Medical Device Incidents

- Medical device incidents or malfunctions of the device that result in an incident will be detected, documented, and reported during all periods of the study in which the medical device is used.
- If the investigator learns of any incident at any time after a participant has been discharged from the study, and such incident is considered reasonably related to a medical device provided for the study, the investigator will promptly notify the sponsor.
- The method of documenting Medical Device Incidents is provided in [Appendix 8](#).

9.2.9.2. Follow-up of Medical Device Incidents

- All medical device incidents involving an AE will be followed and reported in the same manner as other AEs (see Section 9). This applies to all participants, including those who discontinue study treatment or the study.
- The investigator is responsible for ensuring that follow-up includes any supplemental investigations as indicated to elucidate the nature and/or causality of the incident.
- New or updated information will be recorded on the originally completed form with all changes signed and dated by the investigator.

9.2.9.3. Prompt Reporting of Medical Device Incidents to Sponsor

- Medical device incidents will be reported to the sponsor within 24 hours after the investigator determines that the event meets the protocol definition of a medical device incident.
- The Medical Device Incident Report Form will be sent to the sponsor by eCRF. If eCRF is unavailable, then completion of the paper Medical Device Incident Form should be utilized.
- The same individual will be the contact for the receipt of medical device reports and SAE.

9.2.9.4. Regulatory Reporting Requirements for Medical Device Incidents

- The investigator will promptly report all incidents occurring with any medical device provided for use in the study in order for the sponsor to fulfill the legal responsibility to notify appropriate regulatory authorities and other entities about certain safety information relating to medical devices being used in clinical studies.
- The investigator, or responsible person according to local requirements (eg, the head of the medical institution), will comply with the applicable local regulatory requirements relating to the reporting of incidents to the IRB/IEC.

9.3. Treatment of Overdose

An overdose is defined as a dose greater than the doses described in Section 7.1 which results in clinical signs and symptoms. In event of an overdose the participants should be closely monitored for AEs/SAEs and these should be recorded in the eCRF.

GSK does not recommend specific treatment for an overdose for nemiralisib.

Decisions regarding treating the overdose, and dose interruptions or modifications will be made by the investigator in consultation with the Medical Monitor based on the clinical evaluation of the participant.

9.4. Safety Assessments

Planned time points for all safety assessments are provided in the SoA (Section 2).

9.4.1. Physical Examinations

- A complete physical examination will be performed at Screening (Visit 1) and will include, at a minimum, assessments of the Skin, Cardiovascular, Respiratory, Gastrointestinal, and Neurological systems. Height and weight will also be measured and recorded as specified in the SoA (Section 2).
- A brief physical examination will be performed at all other visits and will include, at a minimum, assessments of the skin, lungs, cardiovascular system, and abdomen (liver and spleen).
- Investigators should pay special attention to clinical signs related to previous serious illnesses.

9.4.2. Vital Signs

- Vital signs (pulse rate, blood pressure [systolic and diastolic] and respiratory rate) will be performed as specified in the SoA (Section 2), prior to the spirometry maneuvers and with the participant in the sitting position. The participant must be seated at least 5 minutes before these measurements are performed and a single set of values will be collected.
- Blood pressure and pulse measurements will be assessed with a completely automated device. Manual techniques will be used only if an automated device is not available.
- The vital sign results will be captured in the participant's clinic notes and in the eCRF

9.4.3. Electrocardiograms

Standardized ECG equipment and centralized overreads of the ECGs will be provided to all participating sites by the external provider contracted by GSK.

A 12-lead ECG with a 15-second rhythm strip will be obtained as outlined in the SoA (see Section 2) using an ECG machine that automatically calculates the heart rate and measures PR, QRS, QT, and QTc intervals. Refer to Section 8.1.2 for QTc withdrawal criteria and additional QTc readings that may be necessary.

- For this study, the same QT correction formula (Fridericia's) *must* be used throughout the study for all participants. Safety ECGs and other non-protocol specified ECGs are an exception.
- All ECG measurements will be performed with the participant resting in a supine position for approximately 5 minutes before each reading, which should be carried out after measurement of vital signs and before spirometry.

- The investigator, a designated sub-investigator, or other appropriately trained site personnel, will be responsible for performing the 12-lead ECG recording at each applicable study visit (see SoA [Section 2]).
- All ECGs will be electronically transmitted to an independent cardiologist (contracted by GSK) and evaluated. The independent cardiologist, blinded to treatment assignment, will be responsible for providing measurements of heart rate, QT intervals and an interpretation of all ECGs collected in this study. These results will be provided to the investigator. The investigator is responsible for reviewing ECG reports and attesting to his/her review of the independent cardiologist's assessment.
- A local ECG may be used to assess eligibility criteria however an ECG for central review should also be performed at screening/randomisation. If the central review indicates that the patient is ineligible the patient will be withdrawn from the study.
- Participants with an abnormal ECG reading(s) (exclusionary and non-exclusionary) will be followed/referred to a specialist according to the discretion of the Investigator.
- Details of all cardiac monitoring procedures will be provided by the centralized cardiology service provider.

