1. The start of the SoC for the index exacerbation is defined as the start of either oral/systemic corticosteroids[s] or antibiotic[s] whichever is earliest and is expected to start shortly after diagnosis, though it may already have been started before formal diagnosis of COPD exacerbation. If SoC is started >48 hours prior to diagnosis, the participant is not eligible to participate, but may be re-screened in the future as described in the main protocol.
2. All Screening/baseline assessments should be completed within 48hrs of start of SoC.

12-Week Double-Blind Treatment Period: Once-daily study treatment administration will start on Day 1 (Visit 2).

At the end of the Screening Period (-2 to -1/0 days), participants who meet all of the Inclusion Criteria and none of the Exclusion Criteria will complete Visit 2 (Randomization Visit/Day 1). If a participant meets all of the eligibility criteria, it is possible for him/her to complete the Screening Visit and the Randomization Visit on the same day (e.g., outpatient participant who presents with an acute moderate exacerbation of COPD).

At this visit, participants will be randomized to receive one of the doses of nemoralisib QD or placebo QD in addition to SoC for 12 weeks.

Randomization and the first dose of the double-blind study treatment administration should take place in the morning, as soon as possible following determination of eligibility and completion of the baseline PRO measures, including the EXACT-PRO questionnaire for the day of randomization, and FEV₁ measurement and no later than 48hrs after the start of SoC.

Note: In the event that completion of the assessments/procedures at Visit 2 (or in cases where Visit 1 and Visit 2 are conducted on the same day) extends past noon, the first dose of the double-blind study treatment administration may occur up until 3:00 pm on Day 1. After Day 1, dosing should take place in the morning each day through the end of the 12-Week Double-Blind Treatment Period.

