6. For participants hospitalized for the index exacerbation at Screening, spirometry (as noted in the bullet above) should also be performed in the morning on the day of discharge
7. Pre-dose
8. Single assessment

9. Screening: Due to the short screening window, local laboratory results will be used for purposes of determining subject eligibility for randomization. If local laboratory results are already available within 48 hours from diagnosis of the index COPD exacerbation, these results can be used for determination of subject eligibility; there is no need to take another sample for local analysis. A sample for central laboratory analysis should also be obtained.
10. Presence of hepatitis B surface antigen (HBsAg) and/or positive hepatitis C antibody test result at Screening or within 3 months prior to first dose of study treatment or positive test for HIV antibody is exclusionary. NOTE: Participants with positive Hepatitis C antibody due to prior resolved disease can be enrolled, only if a confirmatory negative Hepatitis C RNA test is obtained. Positive hepatitis C RNA test result at Screening or within 3 months prior to first dose of study treatment is exclusionary. NOTE: Hepatitis C RNA test is optional and participants with negative Hepatitis C antibody test are not required to also undergo Hepatitis C RNA testing. Because of the short window for Screening, double-blind study treatment may start before the results of the hepatitis and HIV tests have been received. If subsequently the test(s) is(are) found to be positive, the participant will need to be withdrawn from study treatment and may also be withdrawn from the study as judged by the Principal Investigator in consultation with the Medical Monitor.
11. If the urine pregnancy text result is positive, a blood sample for serum pregnancy testing will need to be conducted to confirm pregnancy status
12. Approximately 20 mL (4 teaspoons) of blood will be collected in all participants at each time point noted; at Screening, the sample should be collected as soon as possible after the participant has completed the informed consent and PRO assessments
13. Informed consent for optional sub-studies (e.g. genetics research, PK) must be obtained before collecting a sample/performing procedure
14. Collected at Visit 2 or any time post-randomization if unable to collect at Visit 2

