18. **Abnormal Clinically Significant Laboratory Finding:** A clinical abnormality or laboratory parameter(s) which is/are not specifically listed in the exclusion criteria, outside of the reference range for the population being studied may be included if the Investigator (in consultation with the GSK Medical Monitor if required) documents that the finding is unlikely to introduce additional risk factors and will not interfere with the study procedures.
19. **Abnormal Clinically Significant 12-Lead ECG:** abnormal, clinically significant ECG finding (e.g. myocardial Infarction or demonstrating a clinically significant arrhythmia requiring treatment) at Screening (Visit 1) or upon repeat prior to randomization.
20. **QTcF:** QTcF >480 msec for participants with or without Bundle Branch Block, based on averaged QTcF values of triplicate ECGs.
21. **HIV antibody:** A positive test for HIV antibody at Screening.

NOTE: due to time taken to conduct HIV antibody analysis, participants may be randomised to the study before receiving these results. If a participant has a positive test result, they will need be withdrawn promptly from the study

Other Exclusions

22. **Drug/alcohol abuse:** Known or suspected history of alcohol or drug abuse within the last 2 years.
23. **History of regular alcohol consumption:** Defined as an average weekly intake of >28 units for males or >21 units for females within 6 months of Screening (Visit 1). One unit is equivalent to 8 g of alcohol: a half-pint (~240 mL) of beer, 1 glass (125 mL) of wine or 1 (25 mL) measure of spirits.
24. **Potential of non-compliance:** Participants at risk of non-compliance, or unable to comply with the study procedures. Any infirmity, disability, or geographic location that would limit compliance for scheduled visits.

25. **Questionable validity of consent:** Participants with a history of psychiatric disease, intellectual deficiency, poor motivation or other conditions that will limit the validity of informed consent to participate in the study.
26. **Affiliation with investigator site:** Study investigators, sub-investigators, study coordinators, employees of a participating investigator or immediate family members of the aforementioned are excluded from participating in this study.

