8. DISCONTINUATION CRITERIA

A participant may voluntarily discontinue participation in this study at any time (including during the Screening Period, the 12-Week Double-Blind Treatment Period or during the 12-Week Post-Treatment Follow-Up Period). The Investigator may also at his/her discretion discontinue a participant from this study at any time. Every effort should be made by the Investigator to keep the subject in the study.

Participants who are withdrawn from the study will not be replaced and cannot be re-screened.

The primary reason for subject withdrawal will be recorded in the eCRF (see Section 8.2).

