8.1. Discontinuation of Study Treatment

A participant may be discontinued from study treatment but continue in the study for collection of data (including efficacy and safety data) and to minimize missing data. Participants who discontinue from study treatment will move directly into the 12-Week Post Treatment Follow Up Period starting with Visit 7, 28 days following the discontinuation date.

[figure not shown]
If a higher than expected number of participants prematurely discontinues double-blind study treatment or prematurely discontinues from the study, additional participants may be randomized, at the discretion of the Sponsor.

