8.1.2. QTc Stopping Criteria

In this study, GSK is contracting with an external vendor to provide standardized 12-lead ECG equipment and centralized ECG overreads for all participating sites (Section 9.4.3).

The same QT correction formula (Fridericia's) *must* be used throughout the study for all participants. Safety ECGs and other non-protocol specified ECGs are an exception.

The QTc criteria should be based on the averaged QTc value of triplicate ECGs obtained over a brief (e.g., 5-10 minute) recording period.

A participant who meets either bulleted criteria based on the average of triplicate ECG readings will be withdrawn from study treatment:

- QTc >530 msec (with or without underlying Bundle Branch Block) OR Uncorrected QT >600 msec
- Change from baseline of QTc > 60 msec

In addition, participants should be excluded (Screening) or be discontinued from study treatment if they have an abnormal, clinically significant ECG finding as defined in the ECG manual.

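### Section 9.4.3 withdraws from the study any participant found ineligible on central ECG review, even after dosing, and so loses the 12-week follow-up that Section 8.1 gives to those who stop treatment

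*Protocol*

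**What the plan says.** Section 9.4.3 separates the ECG that may decide eligibility from the one that is read centrally: "A local ECG may be used to assess eligibility criteria however an ECG for central review should also be performed at screening/randomisation". It follows with a mandatory rule: "If the central review indicates that the patient is ineligible the patient will be withdrawn from the study". Nothing in the section limits this to participants who have not yet been randomised or dosed.

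Elsewhere the protocol separates stopping treatment from leaving the study:

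- Section 8 gives the general aim: "Every effort should be made by the Investigator to keep the subject in the study".
- Section 8.1 allows a participant to stop treatment and remain in the study, with the stated purpose of limiting missing data: "Participants who discontinue from study treatment will move directly into the 12-Week Post Treatment Follow Up Period starting with Visit 7".
- Section 8.1.2, on ECG findings, says that "participants should be excluded (Screening) or be discontinued from study treatment if they have an abnormal, clinically significant ECG finding".
- Footnote 10 of the treatment-period Schedule of Activities covers another late eligibility failure, positive hepatitis or HIV serology. There "the participant will need to be withdrawn from study treatment and may also be withdrawn from the study as judged by the Principal Investigator", so leaving the study is a matter of judgement.

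On timing, the Synopsis says that for an eligible participant "it is possible for him/her to complete the Screening Visit and the Randomization Visit on the same day". Section 5.1 requires randomisation and the first dose no later than 48 hours after the start of standard of care.

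**The concern.** The rule in 9.4.3 is absolute, and the circumstances in which it applies make it likely to reach people who have already taken study drug. The option to use a local ECG matters mainly when the central read is not yet available. Someone who consents but is never randomised is already a screen failure under Section 6.4, so the rule chiefly concerns randomised participants.

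Once dosed, a participant belongs to the MITT and Safety populations (Section 10.2) whatever the central reader finds. Withdrawal from the study then removes follow-up data from someone who is still analysed. It does so in participants with a cardiac reason for exclusion, where safety follow-up after exposure is of most interest. What is at stake is adverse event, exacerbation and FEV₁ data from Visits 7 to 9, and the ECG and laboratory tests at Visit 7.

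**Working it through.** **Can the central read come after the first dose?** Visits 1 and 2 may be on one day, dosing is due within 48 hours of starting standard of care, and a local ECG is enough to proceed. The protocol gives no turnaround time for the central ECG read. A late read is therefore an inference, but one these provisions plainly allow.

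**What each route provides to a dosed participant:**

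| | Withdrawn from the study (9.4.3) | Treatment stopped (8.1) |
|---|---|---|
| Scheduled visits after stopping | 1 Early Withdrawal Visit, within 24 hours or as soon as possible | Visits 7, 8 and 9, at follow-up Days 28, 56 and 84 |
| Scheduled ECG and laboratory tests | once, at Early Withdrawal | once, at Visit 7 |
| Adverse event and exacerbation collection | to Early Withdrawal | 84 / 7 = 12 weeks |
| FEV₁ | once, at Early Withdrawal | at each of 3 visits |

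The loss per affected participant is 3 follow-up visits and 12 weeks. For every 10 such participants it is 10 × 3 = 30 visits and 10 × 12 = 120 participant-weeks.

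The single ECG on each route is not equivalent. Appendix 5 takes 10 days (5 half-lives) as the time to eliminate the drug. An Early Withdrawal ECG taken on time falls inside that period, whereas the Visit 7 ECG, 28 days after stopping, falls well after it.

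**Where the texts overlap.** Exclusion 20 bars "QTcF >480 msec for participants with or without Bundle Branch Block", averaged over triplicate ECGs. The treatment stopping limits in 8.1.2 are QTc >530 msec, uncorrected QT >600 msec, or a rise in QTc of more than 60 msec.

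- For a baseline QTcF above 480 and up to 530 msec, a band of 530 − 480 = 50 msec, only 9.4.3 speaks on the QTc value, so there is no textual conflict. The result is still odd: this participant gets less follow-up than one who passes 530 msec on drug.
- For a clinically significant baseline abnormality read after dosing, or a baseline value beyond the 8.1.2 limits, 9.4.3 says leave the study while 8.1.2 can be read as stop treatment only.

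**How many, and does it touch power?** The protocol gives no rate of central ECG ineligibility after dosing. Take 0.5% to 5% as an assumed range:

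- Affected overall: 1,250 × 0.005 = 6.25 to 1,250 × 0.05 = 62.5, about 6 to 63.
- Per 340-participant arm: 340 × 0.005 = 1.7 to 340 × 0.05 = 17.

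For the key secondary endpoint, first reproduce the 76% in Section 10.1.2. Use a normal approximation to the log rate ratio, with placebo rate 0.51, active rate 0.51 × 0.75 = 0.3825, dispersion 3.5 in each arm and n = 340 per arm. Success at >80% posterior probability is treated as a one-sided 0.20 test:

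- Variance = (1/0.51 + 3.5 + 1/0.3825 + 3.5) / 340 = 11.575 / 340 = 0.0340; standard error 0.1845.
- Φ(0.2877 / 0.1845 − 0.8416) = Φ(0.718) = 76.3%, which agrees with the stated 76%.

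Removing the affected participants entirely, which is worse than what would happen, gives 76.2% at 0.5% (n = 338.3) and 75.1% at 5% (n = 323). Power is not the issue.

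**The case against.** The strongest reply is that 9.4.3 contradicts nothing. The ECG in question is scheduled at Visit 1, so a central read of it is a screening finding. It fits the exclusion branch of the 8.1.2 sentence at least as well as the discontinuation branch. The 8.1.2 limits use the mean of triplicates, whereas the scheduled screening ECG is a single recording. Section 8.1 is permissive, and Section 8 also lets the investigator remove a participant at any time. Exclusions 9 and 21 and Section 9 withdraw participants with positive virology from the study, so footnote 10 is the outlier and 9.4.3 follows the more common rule.

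Nor is bias to be expected. The disqualifying ECG is scheduled before dosing and read by a cardiologist blinded to treatment, so loss should not differ by arm. Safety is partly covered: the Early Withdrawal Visit includes ECG, vital signs, laboratory tests and adverse event review; serious events are followed to resolution; and 9.4.3 allows specialist referral at the investigator's discretion. The key secondary model has an offset for time in study, so partial exposure still counts. Visits 7 to 9 mainly serve exploratory endpoints.

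Much of this stands. There is no strict contradiction for QTcF of 480 to 530 msec, footnote 10 is a weak comparator, no bias between arms is shown, and the numbers are unknown. None of it returns the lost visits or gives a reason to lose them. Whichever branch of 8.1.2 applies, a participant who has taken drug and remains in two analysis populations is followed for less time than Section 8.1 provides for everyone else who stops treatment.

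**Conclusion.** The concern holds and is minor. As written, 9.4.3 requires study withdrawal of a dosed participant found ineligible on central ECG review. It costs 3 scheduled visits and 12 weeks of follow-up per affected participant, including the only scheduled ECG and laboratory tests after the drug has cleared.

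Safety follow-up is shortened, not abolished. The Day 84 treatment-period visit is not restored by either route. For someone stopped in the first few days, however, Visit 9 falls 84 days later, so Visits 7 to 9 would have covered most of the 12-week exacerbation window.

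The conclusion assumes that the central read sometimes arrives after the first dose. The protocol permits this but does not say how often it happens. The number affected is probably small, and even at an assumed 5% the key secondary probability of success falls by about one percentage point.

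**What to change.** Replace the withdrawal sentence in 9.4.3 with a rule in two parts. A participant already dosed who is found ineligible on central ECG review discontinues study treatment and enters the 12-Week Post-Treatment Follow-Up Period as in 8.1, unless consent is withdrawn. Withdrawal from the study applies only to participants not yet dosed.

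The cost is one sentence and at most 3 visits per affected participant, of a kind already scheduled for those who stop treatment. If the sponsor wants a single rule for all late-detected ineligibility, the virology wording in Exclusions 9 and 21 and in Section 9 would need the same change. The ECG correction does not depend on that.
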